2.7 Correlative Science Objectives

- 2.7.1** To analyze polymorphisms in MDM2 and in genes including TP53, ATM, TGFB1, IL4, IL6, and IL10 and determine correlations with a higher likelihood of adverse radiation reactions (radiation sensitivity) and with toxicities
- 2.7.2** To analyze polymorphisms in MDM2 and in genes including TP53, ATM, TGFB1, IL4, IL6, and IL10 to determine correlations with secondary endpoints such as local-regional control.

3.0 PATIENT SELECTION

For questions regarding eligibility criteria, see the Study Resources page. Please note that the Study Chair cannot grant waivers to eligibility requirements.

3.1 On-Study Guidelines

This clinical trial can fulfill its objectives only if patients appropriate for this trial are enrolled. All relevant medical and other considerations should be taken into account when deciding whether this protocol is appropriate for a particular patient. Physicians should consider the risks and benefits of any therapy, and therefore only enroll patients for whom this treatment is appropriate.

Physicians should consider whether any of the following may render the patient inappropriate for this protocol:

- Psychiatric illness which would prevent the patient from giving informed consent.
- Medical condition such as uncontrolled infection (including HIV), uncontrolled diabetes mellitus or cardiac disease which, in the opinion of the treating physician, would make this protocol unreasonably hazardous for the patient.
- Women of reproductive potential should agree to use an appropriate method of birth control throughout their participation in this study due to the teratogenic potential of the therapy utilized in this trial. Appropriate methods of birth control include abstinence, oral contraceptives, implantable hormonal contraceptives or double barrier method (diaphragm plus condom).
- Medical conditions, genetic mutations or active medications that might make the patient more susceptible to radiation toxicity.

3.2 Eligibility Criteria

Use the spaces provided to confirm a patient's eligibility by indicating Yes or No as appropriate. It is not required to complete or submit the following page(s).

When calculating days of tests and measurements, the day a test or measurement is done is considered Day 0. Therefore, if a test were done on a Monday, the Monday one week later would be considered Day 7.

_____ **3.2.1 Histologically confirmed invasive carcinoma of the breast** of any of the following histologies (ductal, lobular, mammary, medullary, or tubular). Patients with metaplastic breast cancer are not eligible.

_____ **3.2.2 Patients will be staged according to the TNM staging system.**

For patients *not* receiving neoadjuvant chemotherapy, pathologic staging must be T0N1-2a, T1N1-2a, T2N1-2a, T3N0-2a, and all M0 status.

For patients receiving neoadjuvant chemotherapy, clinical pre-chemo staging and post mastectomy pathological staging is required for all patients. Patients who have received neoadjuvant chemotherapy and are pathologically cT0-2 and N0 are only eligible if biopsy-proven clinically N1 or N2 disease is documented prior to the start of neoadjuvant chemotherapy. cT3N0 patients or ypT3N0 patients who receive neoadjuvant chemotherapy may be eligible based on clinical or pathological T stage, and do not require pathologically positive lymph nodes.

Note: Higher of the clinical or pathological T and N stage are used for final staging, if receiving neoadjuvant chemotherapy.

All patients with clinical, radiographic or pathological T4, N3 or involved internal mammary disease (N1b, N1c, and N2b) are not eligible. **N1mic patients are eligible.**

_____ **3.2.3 No prior therapeutic radiation therapy to the chest, neck or axilla. Prior radioactive oral iodine is permitted.**

_____ **3.2.4 No prior history of ipsilateral breast cancer (invasive disease or DCIS).** LCIS and benign breast disease is allowed.

_____ **3.2.5 No history of prior or concurrent contralateral invasive breast cancer.** Benign breast disease, LCIS or DCIS of contralateral breast is allowed.

_____ **3.2.6 No active collagen vascular diseases**, such as: systemic lupus erythematosus, scleroderma, or dermatomyositis.

_____ **3.2.7 Negative inked histologic margins from mastectomy pathology** (no invasive cells at margin). **Patients with DCIS at margin are eligible.**

_____ **3.2.8 No significant post mastectomy complications in the ipsilateral or contralateral breast requiring an unplanned re-operation or admission for IV antibiotics.** Re-operation for margins evaluation, nodal completion and routine reconstruction is acceptable.

_____ **3.2.9 Radiation oncologist intends to treat all target volumes described in section 7.4 and respect all normal tissues identified in section 7.4.3 in accordance with the dosimetric constraints described** (simulation before registration recommended).

_____ **3.2.10 Radiation oncologist is planning to treat regional lymph nodes including internal mammary nodes and meet acceptable protocol dosimetric requirements.**

_____ **3.2.11 Radiation oncologist is NOT planning to utilize a chest wall/scar boost.**

- _____ **3.2.12 Patient must have undergone immediate reconstruction at the time of mastectomy or be planning to undergo reconstruction within 18 months after radiation.**
- _____ **3.2.13 Treating physician and patient must plan to start radiation treatment within the timeframes specified in Section 7.0.**
- _____ **3.2.14 If a tissue expander is utilized it needs to be a fluid filled expander, NO air expander (unless completely deflated) during radiation therapy.**
- _____ **3.2.15 For patients with diabetes, hemoglobin A1C test must have been performed ≤ 90 days prior to registration.**
- _____ **3.2.16 No co-existing medical conditions with life expectancy < 5 years.**
- _____ **3.2.17 No other malignancy within 5 years of registration** with the exception of basal cell or squamous cell carcinoma of the skin treated with local resection only or carcinoma in situ of the cervix.
- _____ **3.2.18 Negative pregnancy test (serum or urine HCG) in women of child-bearing potential ≤ 7 days prior to registration.** Patients who have received a bilateral tubal ligation still require a negative pregnancy test for eligibility.

A female of childbearing potential is a sexually mature female who has not undergone a hysterectomy or bilateral oophorectomy and has not been naturally postmenopausal for at least 12 consecutive months.
- _____ **3.2.19 Women of child-bearing potential must agree to utilize a form of birth control or agree to undergo sexual abstinence during radiation therapy.**
- _____ **3.2.20 ECOG (Zubrod) Performance Status 0-1**
- _____ **3.2.21 Patient ≥ 18 years of age**
- _____ **3.2.22 Patients must be able to read and comprehend English, in order to be able to complete study questionnaires.** However, patients participating through CCTG institutions who can read and comprehend French are eligible.

4.0 PATIENT REGISTRATION

4.1 Investigator and Research Associate registration with CTEP

Food and Drug Administration (FDA) regulations and National Cancer Institute (NCI) policy require all individuals contributing to NCI-sponsored trials to register and renew their registration annually. To register, all individuals must obtain a Cancer Therapy Evaluation Program (CTEP) Identity and Access Management (IAM) account at [REDACTED]. In addition, persons with a registration type of Investigator (IVR), Non-Physician Investigator (NPIVR), or Associate Plus (AP) must complete their annual registration using CTEP's web-based Registration and Credential Repository (RCR) at [REDACTED].

RCR utilizes five person registration types.

- **IVR**—MD, DO, or international equivalent;
- **NPIVR**—advanced practice providers (e.g., NP or PA) or graduate level researchers (e.g., PhD);
- **AP**—clinical site staff (e.g., RN or CRA) with data entry access to CTSU applications such as the Roster Update Management System (RUMS), OPEN, Rave; acting as a primary site contact, or with consenting privileges
- **Associate (A)**—other clinical site staff involved in the conduct of NCI-sponsored trials; and
- **Associate Basic (AB)**—individuals (e.g., pharmaceutical company employees) with limited access to NCI-supported systems.

RCR requires the following registration documents:

Documentation Required	IVR	NPIVR	AP	A	AB
FDA Form 1572	✓	✓			
Financial Disclosure Form	✓	✓	✓		
NCI Biosketch (education, training, employment, license, and certification)	✓	✓	✓		
GCP training	✓	✓	✓		
Agent Shipment Form (if applicable)	✓				
CV (optional)	✓	✓	✓		

An active CTEP-IAM user account and appropriate RCR registration is required to access all CTEP and Cancer Trials Support Unit (CTSUS) websites and applications. In addition, IVRs and NPIVRs must list all clinical practice sites and Institutional Review Boards (IRBs) covering their practice sites on the FDA Form 1572 in RCR to allow the following:

- Addition to a site roster;
- Assign the treating, credit, consenting, or drug shipment (IVR only) tasks in OPEN;
- Act as the site-protocol Principal Investigator (PI) on the IRB approval; and
- Assign the Clinical Investigator (CI) role on the Delegation of Tasks Log (DTL).

In addition, all investigators acting as the Site-Protocol PI (investigator listed on the IRB approval), consenting/treating/drug shipment investigator in OPEN, or as the CI on the DTL must be rostered at the enrolling site with a participating organization.

Additional information is located on the CTEP website at [REDACTED] For questions, please contact the **RCR Help Desk** by email at [REDACTED]

4.2 CTSU Site Registration Procedures

This study is supported by the NCI Cancer Trials Support Unit (CTSU).

IRB Approval:

For CTEP and Division of Cancer Prevention (DCP) studies open to the National Clinical Trials Network (NCTN) and NCI Community Oncology Research Program (NCORP) Research Bases after March 1, 2019, all U.S.-based sites must be members of the NCI Central Institutional Review Board (NCI CIRB). In addition, U.S.-based sites must accept the NCI CIRB review to activate new studies at the site after March 1, 2019. Local IRB review will continue to be accepted for studies that are not reviewed by the CIRB, or if the study was previously open at the site under the local IRB. International sites should continue to submit Research Ethics Board (REB) approval to the CTSU Regulatory Office following country-specific regulations.

Sites participating with the NCI CIRB must submit the Study Specific Worksheet for Local Context (SSW) to the CIRB using IRBManager to indicate their intent to open the study locally. The NCI CIRB's approval of the SSW is automatically communicated to the CTSU Regulatory Office, but sites are required to contact the CTSU Regulatory Office at [REDACTED] to establish site preferences for applying NCI CIRB approvals across their Signatory Network. Site preferences can be set at the network or protocol level. Questions about establishing site preferences can be addressed to the CTSU Regulatory Office by emailing the email address above or calling [REDACTED]

Sites using their local IRB or REB, must submit their approval to the CTSU Regulatory Office using the Regulatory Submission Portal located in the Regulatory section of the CTSU website. Acceptable documentation of local IRB/REB approval includes:

- Local IRB documentation;
- IRB-signed CTSU IRB Certification Form; and/or
- Protocol of Human Subjects Assurance Identification/IRB Certification/Declaration of Exemption Form.

In addition, the Site-Protocol Principal Investigator (PI) (i.e. the investigator on the IRB/REB approval) must meet the following criteria in order for the processing of the IRB/REB approval record to be completed:

- Holds an Active CTEP status;
- Rostered at the site on the IRB/REB approval and on at least one participating roster;
- If using NCI CIRB, rostered on the NCI CIRB Signatory record;
- Includes the IRB number of the IRB providing approval in the Form FDA 1572 in the RCR profile; and
- Holds the appropriate CTEP registration type for the protocol.

4.2.1 Additional site registration requirements

Additional requirements to obtain an approved site registration status include:

- An active Federal Wide Assurance (FWA) number;
- An active roster affiliation with the Lead Protocol Organization (LPO) or a Participating Organization (PO); and
- Compliance with all protocol-specific requirements (PSRs).

4.2.2 Downloading Site Registration Documents

Download the site registration forms from the protocol-specific page located on the CTSU members' website. Permission to view and download this protocol and its supporting documents is restricted based on person and site roster assignment. To participate, the institution and its associated investigators and staff must be associated with the LPO or a Protocol Organization (PO) on the protocol. One way to search for a protocol is listed below.

- Log in to the CTSU members' website [REDACTED] using your CTEP-IAM username and password;
- Click on *Protocols* in the upper left of the screen
 - Enter the protocol number in the search field at the top of the protocol tree, or
 - Click on the By Lead Organization folder to expand, then select *Alliance*, and protocol number [A221505].
- Click on *Documents*, select *Site Registration*, and download and complete the forms provided. (Note: For sites under the CIRB, IRB data will load automatically to the CTSU.)

4.2.3 Protocol Specific requirements for A221505 Site Registration

IROC Credentialing Status Inquiry (CSI) Form – this form is submitted to IROC Houston to verify credentialing status or to begin a new modality credentialing process.

4.2.4 Submitting Regulatory Requirements

Submit required forms and documents to the CTSU Regulatory Office using the Regulatory Submission Portal on the CTSU website.

To access the Regulatory Submission Portal log in to the CTSU members' website, go to the Regulatory section and select Regulatory Submission.

Institutions with patients waiting that are unable to use the Regulatory Submission Portal should alert the CTSU Regulatory Office immediately at [REDACTED] in order to receive further instruction and support.

4.2.5 Checking Your Site's Registration Status

Site registration status may be verified on the CTSU members' website.

- Click on *Regulatory* at the top of the screen;
- Click on *Site Registration*; and
- Enter the site's 5-character CTEP Institution Code and click on Go.
 - Additional filters are available to sort by Protocol, Registration Status, Protocol Status, and/or IRB Type.

Note: The status shown only reflects institutional compliance with site registration requirements as outlined within the protocol. It does not reflect compliance with protocol requirements for individuals participating on the protocol or the enrolling investigator's status with NCI or their affiliated networks.

4.2.6 Credentialing

See [Section 14.0](#) for credentialing requirements.

4.3 Patient Registration Requirements

All patients must have completed mastectomy prior to registration, and must be registered prior to initiation of radiation therapy.

- **Informed consent:** the patient must be aware of the neoplastic nature of his/her disease and willingly consent after being informed of the procedure to be followed, the experimental nature of the therapy, alternatives, potential benefits, side-effects, risks, and discomforts. Current human protection committee approval of this protocol and a consent form is required prior to patient consent and registration.
- **Patient completed booklets:** Patient questionnaire booklets are to be ordered prior to the registration of any patients. Patient questionnaire booklets can be ordered by downloading and completing the CTSU supply request form (located under the site registration documents section of the A221505 CTSU site) and submitting the form through the CTSU regulatory portal. Samples of the assessments are found in Appendices II-V, which are to be used for reference and IRB submission only. They are not to be used for patient completion.

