5.0 STUDY CALENDAR

The pre-study testing intervals are guidelines only. Laboratory and clinical parameters during treatment are to be followed using individual institutional guidelines and the best clinical judgment of the responsible physician. It is expected that patients on this study will be cared for by physicians experienced in the treatment and supportive care of patients on this trial.

Pre-Study Testing Intervals

- To be completed ≤ 7 DAYS before registration: Pregnancy test,
- To be completed ≤ 28 DAYS before registration: history and physical.

	Prior to Registration	Before RT [¥]	At completion of RT [€]	2 to 8 weeks post RT	6, 12, 18 mos. post RT*	2 years post RT*	30 mos., 3,4 and 5 years post RT**	10 and 15 years post RT***
Tests & Observations								
H&P, Weight, PS	X	X (1)	X	X	X	X	X	
Height	X							
Mastectomy or reconstruction complications		X	X	X	X	X	X	
Recurrence (scan or clinical) Assessment					X	X	X	X
Adverse Events Assessment		A	A	A	A	A	A	
Clinical Lymphedema Assessment		B	B	B	B	B	B	
Cardiac and Brachial Plexopathy Events					C	C	C	C
Arm Circum. Measure (see §10.5)		X			X (2)	X		
Photographs for Cosmetic Assessment		D				X (4)		
Laboratory Studies								
Serum or Urine HCG	E							
Hemoglobin A1C	F							
Questionnaires								
Breast-Q Post-mastectomy		G						
Breast-Q Post-reconstruction		G				X	X (3)	
LBCQ		X			X (2)	X	X (3)	
BLE		H			X (2)	X	X (3)	
Economic Surveys		I	J	I	J			
EQ-5D-3L		X			X	X		
Was It Worth It Questionnaire						X		
Correlative Study (optional)	To be collected at baseline, see Sections 6.2 and 13.1							
Whole Blood								

¥ May be completed at any time following patient consent (before or after registration, but prior to treatment)

€ May be completed within 72 hours of last radiation treatment.

* +/- 6 weeks.

** For 30-month visit, +/- 6 weeks; for 3, 4, and 5-year visits, +/- 3 months

*** +/- 6 months. All follow up, including survival status, done after 5 years will be gathered by record review only.

A Assessment of side effects related to radiation therapy should be assessed according to the history and physical examination.

B To be assessed per the CTCAE criteria.

C Will be assessed by medical record review.

D Only for patients with final reconstruction completed before radiation.

E For women of childbearing potential. Must be done within 7 days prior to registration.

F For diabetic patients only, to be done ≤ 90 days before registration.

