7.0 TREATMENT PLAN/INTERVENTION

Radiation treatment may begin no sooner than 21 days after initial surgery or 21 days after the completion of adjuvant chemotherapy. Radiation therapy must begin no later than 84 days (12 weeks) after initial surgery or the completion of adjuvant chemotherapy, whichever is later.

- **Initial surgery** is defined as mastectomy and any subsequent surgeries related to the initial mastectomy, including additional margin resection, lymph node removal or immediate reconstruction. If neoadjuvant chemotherapy is used, then surgery must occur within 56 days after completing the cytotoxic component of therapy.
- **Chemotherapy** is defined as cytotoxic chemotherapy, not biological therapy, such as trastuzumab, pertuzumab, etc. Trastuzumab emtansine (Kadcyla) is classified as biological therapy for the purposes of this protocol and NOT chemotherapy.

Randomization: Patients will be randomized to either radiation in 25 fractions over 5-6 weeks or hypofractionation radiation in 16 fractions over 3-4 weeks. Radiation will be delivered to the chest wall/reconstructed breast and regional lymph nodes. The treating radiation oncologist must certify intent to treat regional lymphatics prior to registration.

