7.3 Systemic Therapy

Any **adjuvant hormonal therapy** is allowed. It may begin any time relative to the radiation, at the discretion of the treating physician.

Chemotherapy is allowed. If adjuvant chemotherapy is indicated, it can be delivered before or after radiation therapy. Neoadjuvant chemotherapy is allowed. Patients may be co-enrolled on systemic therapy trials, if there is no contraindication on the other trial.

Cytotoxic systemic therapy may not be used concurrently with radiation, however, trastuzumab, pertuzumab or other biological therapy may be given concurrently per standard of care. Trastuzumab emtansine (or Kadcyla) will be considered a biological therapy and can therefore be given concurrently with radiation treatment.

After finishing cytotoxic chemotherapy, a minimum of 21 days must elapse before the start of radiation. If cytotoxic chemotherapy is started after radiation, a minimum of 21 days must pass after the last fraction of radiation before beginning chemotherapy.

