7.4 Radiotherapy

All radiation therapy questions should be directed to the Alliance A221505 Radiation Co-Chairs.

The radiation methods and dose volume parameters are adapted from RTOG criteria, as outlined in the RTOG breast atlas: [REDACTED]

Radiation therapy treatment planning should begin after consultation with the radiation oncologist and prior to radiation treatment.

A deviation unacceptable will be scored for failure to prescribe proper dose and not treating the required regional lymph nodes, including IMs.

The use of a radiation chest wall or scar boost is not allowed on this trial. If the radiation oncologist feels that a particular patient must receive a scar boost, she should not be enrolled on this trial. Use of a scar boost on an enrolled patient will be scored as a deviation unacceptable, but these patients will still be followed.

Every attempt should be made to meet dose constraints. If dose constraints are not met, patients will remain on protocol treatment unless in unusual circumstances it is recommended that they be removed from protocol treatment by a radiation co-chair. It is recommended this be discussed with a radiation co-chair prior to starting radiation.

Patients will be registered after mastectomy and randomized to one of the following study treatment arms:

Arm 1: Conventional fractionation radiation to the chest wall or reconstructed breast, supraclavicular fossa, axilla and internal mammary nodal basin. 50 Gy in 25 daily 2 Gy fractions. Treatment will be given 5 days a week for 5-6 weeks (no treatment weekends and holidays).

Arm 2: Hypofractionated radiation to the chest wall or reconstructed breast, supraclavicular fossa, axilla and internal mammary nodal basin. 42.56 Gy in 16 daily 2.66 Gy fractions. Treatment will be given 5 days a week for 3-4 weeks (no treatment weekends and holidays).

In the case of a departmental holiday, RT may be given 4 days a week. In case of medical illness or RT side effect(s), treatment breaks are allowed as needed per standard practice.

For both randomized treatment arms, radiation is to be delivered to the following planning target volumes: the reconstructed breast/chest wall, undissected axilla*, supraclavicular fossa and internal mammary nodal chain in the first 3 intercostal spaces.

* The undissected axilla typically includes the high level II and Level III nodes. If an axillary dissection has been performed, RT will only be directed to the un-dissected axilla.

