11.2 Criteria for discontinuation of protocol treatment

Radiation treatment will continue unless one of the following criteria applies:

- Disease progression or relapse
- General or specific changes in the patient's condition render the patient unacceptable for further treatment in the judgment of the treating physician
- Patient withdrawal or non-compliance
- Patient receives alternative treatment (non protocol treatment that replaces standard RT or RT not per protocol) before or during protocol treatment period
- Patient experiences reconstruction related complications to the ipsilateral breast prior to start of radiation. No further follow up will be required for these patients (see Section 11.4.2).

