12.2 Sample Size, Accrual Time and Study Duration

Our target sample size will be 792 evaluable patients (396 in each arm). To account for 10% drop-out due to cancellations or protocol deviations, our target accrual is 880 patients (440 per arm) (90% of 880 is 792).

The study design is a randomized, un-blinded, non-inferiority trial. It is assumed that the two-year breast reconstruction complication rate for the control arm (Arm 1: standard fractions) is 25%. Other assumptions for the sample size determination include:

- α (one-sided) = 0.025
- power = 90%
- non-inferiority margin: the absolute increase in the proportion of patients who experience
- a breast reconstruction complication within two-years is 10% above that of the control arm.
- one interim analysis (when 30% of the information is obtained) for futility

Under an alternative hypothesis that the true rates in the two arms are equal, a sample size of 792 (396 per arm) evaluable patients would give us 90% power to reject the null hypothesis of inferiority. The final analysis will take place after all patients have reached two years post-radiation. The anticipated accrual period is approximately 30 months, and the total study duration is approximately 60 months. We anticipate being able to accrue approximately 30 patients per month based on our best estimate extrapolated from recently closed intact breast trials looking at similar fractionations. It should be noted that if we instead assumed a complication rate of 50% in the control arm (the most statistically conservative, in terms of sample size), the above sample size would still give us approximately 80% power to reject the null hypothesis of inferiority (again with one-sided α of 0.025).

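### No limit is set on the interval from randomisation to the first radiation fraction, so reconstruction complications in that gap become post-randomisation removals in an open-label non-inferiority trial

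*Combined protocol and SAP*

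**What the plan says.** **When patients are randomised.** Section 4.3: "All patients must have completed mastectomy prior to registration, and must be registered prior to initiation of radiation therapy". Section 7.4: "Patients will be registered after mastectomy and randomized to one of the following study treatment arms". Section 12.1 describes the trial as un-blinded.

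**When radiation must start.** Section 7.0: "Radiation therapy must begin no later than 84 days (12 weeks) after initial surgery or the completion of adjuvant chemotherapy, whichever is later". Section 7.3 on systemic treatment: "If adjuvant chemotherapy is indicated, it can be delivered before or after radiation therapy". Eligibility item 3.2.13 asks only for a plan to meet the 7.0 window, and 3.2.9 recommends, without requiring, simulation before registration.

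**Complications before registration.** Item 3.2.8 requires: "No significant post mastectomy complications in the ipsilateral or contralateral breast requiring an unplanned re-operation or admission for IV antibiotics".

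**Complications after registration but before radiation.** Section 11.2 lists as a reason to end protocol treatment: "Patient experiences reconstruction related complications to the ipsilateral breast prior to start of radiation". It adds that these patients need no more follow-up, and 11.4.2 closes them out with an end of study form.

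**Analysis.** Section 12.3.2 makes the primary analysis intent-to-treat, with all randomised patients included. The endpoint is a complication within two years of the end of radiation. Section 12.2 inflates accrual with this reason: "To account for 10% drop-out due to cancellations or protocol deviations".

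**Baselines.** Footnote ¥ of the Section 5.0 calendar governs the column of assessments before radiation: "May be completed at any time following patient consent (before or after registration, but prior to treatment").

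**The concern.** The start-of-radiation clock runs from surgery or from the end of adjuvant chemotherapy, never from randomisation. A patient can be randomised soon after mastectomy, receive adjuvant chemotherapy, and only then approach radiation. Reconstruction complications in that interval happen before either schedule has begun, so they say nothing about fractionation, but they happen after the arm is known.

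Two things are at stake. First, randomised patients who receive neither schedule pull the arms together if they are kept in the analysis. In a non-inferiority test that favours the claim being tested. Second, the decision that a complication ends protocol treatment is made by staff who know the allocation, and it also ends follow-up. The intent-to-treat set then contains patients with no radiation end date from which to count two years, no required outcome data and no stated scoring rule. Randomising close to radiation would turn most of these cases into exclusions before allocation.

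**Working it through.** **1. Length of the gap.**
- Without adjuvant chemotherapy before radiation: up to 84 days (84/30.44 = 2.8 months) from initial surgery. It is about 12 weeks rather than exactly 12, because 7.0 counts later related operations as part of initial surgery.
- With it: chemotherapy duration plus up to 84 days. The documents give no duration. Assuming 8 to 24 weeks and registration as chemotherapy starts, the gap is 8×7 + 84 = 140 days to 24×7 + 84 = 252 days (4.6 to 8.3 months).

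**2. The plan's own figures (12.2).** Inputs: 25% in both arms, margin 0.10, one-sided α 0.025, power 90%.
- n per arm = (1.960 + 1.282)² × 2 × 0.25 × 0.75 / 0.10² = 394.03, rounded up to 395 (total 790, against 792 stated).
- At 396 per arm, SE = √(2 × 0.1875/396) = 0.0308, and power = Φ(0.10/0.0308 − 1.96) = 90.1%. The 12.3.2 simulation gives 90.84%.
- 792/0.90 = 880.
- At 25% v 35% the true difference equals the margin, so the chance of declaring non-inferiority is 2.5%. Allowing for the futility look it is 2.49%; the 12.3.2 simulation gives 2.37%.

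The sample-size arithmetic is therefore sound.

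**3. Dilution if never-irradiated patients are kept.** Let a share r of each arm be never irradiated, with the same event rate c in both arms. The arm rates become 0.25(1 − r) + rc and 0.35(1 − r) + rc, so the difference is 0.10(1 − r) whatever c is. Then

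P(declare non-inferior) = Φ(0.10r/SE − 1.96), with SE close to √((0.1875 + 0.2275)/396) = 0.0324.

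| r (assumed) | patients of 880 | 0.10r/SE | 396 per arm, c from 0 to 100% | 440 per arm, c from 0 to 100% |
|---|---|---|---|---|
| 1% | 9 | 0.031 | 2.7% | 2.7% |
| 2% | 18 | 0.062 | 2.9% | 2.9% |
| 5% | 44 | 0.154 | 3.5–3.6% | 3.6% |
| 10% | 88 | 0.309 | 4.8–5.0% | 4.9–5.2% |

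The 440 column is shown because patients kept in the analysis belong to the randomised total and not to the 396 left after drop-out. The choice matters little. In round figures the error is 2.7%, 2.9%, 3.6% and 5.0%.

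**4. The complication rules side by side.**
- 3.2.8: either breast; unplanned re-operation or admission for IV antibiotics.
- 10.1: ipsilateral; Baker III–IV contracture, complete implant or flap failure, any unplanned reconstruction-related admission, or unplanned return to the operating room.
- 11.2 and 11.4.2: reconstruction-related complications (11.2 specifies the ipsilateral breast), with no severity threshold and no reference to 10.1 or 3.2.8.

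Even if 11.2 is read through 10.1, it does not match 3.2.8. A Baker III contracture without surgery, or an admission for pain, meets 10.1 but not 3.2.8.

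**The case against.** **The removal rule may not be loose.** A reader might infer that any minor complication ends protocol treatment after registration. The documents do not establish that. Section 10.1 defines ipsilateral reconstruction complications as serious events, and 9.2.3 sets routine revisions aside. If 10.1 governs 11.2, the rule overlaps heavily with 3.2.8. What stands is that 11.2 does not say so, and the lists differ in any case.

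**The patient is rechecked before radiation.** A reader might infer that entry checks are stale by the time of radiation. The Section 5.0 calendar repeats the history and physical, weight and performance status before radiation (not needed again if done within 30 days), and has a complication check in the same column. What stands is narrower: footnote ¥ lets the baseline arm volume and EQ-5D be taken any time after consent, possibly before chemotherapy, and both are secondary measures.

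**Registration may in practice be late.** Simulation before registration is recommended, and the radiation oncologist must already intend to treat the specified volumes. A gap of many months applies only to patients registered before adjuvant chemotherapy, and their share is not given. This limits the size of the problem but sets no bound on the interval.

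**The rates are assumed.** No document gives a removal rate before radiation. At 1–2% the error stays close to nominal, and the 10% case equals the whole drop-out allowance. This stands in full.

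**The follow-up conflict would remain.** Complications inside a short window would still end follow-up while 12.3.2 analyses everyone. That is correct, so the fix has to cover both.

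**Conclusion.** The point holds as a design weakness that is cheap to improve; it is not an error in the sample size. The interval from randomisation to radiation is unlimited in the text, bounded only indirectly at about 12 weeks without adjuvant chemotherapy and longer with it. Complications in that interval end treatment and follow-up with the arm known, and the intent-to-treat statement is not reconciled with this.

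The size depends on a removal rate the documents do not give. The error at 25% v 35% is 2.7–2.9% for removals of 1–2%, 3.6% at 5% and about 5.0% at 10%. This assumes equal removal in both arms, a common event rate, and removed patients kept in the analysis with an outcome.

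A reader might go further and infer that removals will differ by arm and bias the result towards non-inferiority. Knowledge of the arm makes that possible, but neither schedule has begun, so fractionation cannot cause the complications, and unplanned admissions or re-operations leave limited room for judgement. Nothing in the documents supports a figure for it. Such a bias would also arise from dropping patients, so it cannot be added to a dilution effect that requires keeping them.

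**What to change.** 1. In 4.3, keep early consent, but require registration and randomisation after any adjuvant chemotherapy that precedes radiation and within a short stated window before the planned first fraction. Twenty-eight days is one example, matching the interval the calendar already uses for the history and physical before registration. Item 3.2.8 then screens most of these complications before allocation.
2. Take the arm-volume and EQ-5D baselines under footnote ¥ in the same window.
3. Reconcile the complication definitions in 3.2.8, 10.1, 11.2 and 11.4.2, with explicit cross-references.
4. For removals that remain, reconcile the end of follow-up in 11.2 and 11.4.2 with the intent-to-treat set in 12.3.2, and state how those patients are followed and scored.

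The cost is protocol wording. Some registrations move later, and some consented patients are lost before randomisation instead of after it. The 792 and 880 targets are unchanged, and no extra patients or procedures are needed.
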